1.1.2 Dexamethasone solution for Oral Inflammatory Ulcerative Diseases

The efficacy of dexamethasone solution has been well described in several clinical trials. Rhodus et al. conducted a prospective controlled clinical trial to test the efficacy of dexamethasone solution in 13 patients with oral erosive-ulcerative lichen planus²⁷. Patients were instructed to rinse with 5 ml of dexamethasone 0.1% solution for 3 min and then to expectorate. Subjective symptomatology (pain and/or discomfort) was recorded on a 100 mm visual analogue scale (VAS) at first visit and at 6 week follow up. Patients experienced significant subjective improvement in symptoms following the dexamethasone treatment (VAS score pre-treatment: 6.7 ± 1.4 ; VAS score post-treatment: 2.3 ± 0.6).

Hambly et al. conducted a single-blinded, cross-over pilot trial in nine patients to compare the efficacy of compounded dexamethasone solution for OLP²⁸. Patients were instructed to rinse with 2 ml of dexamethasone 0.5 mg/2 mL compounded as a solution or one 0.5 mg tablet crushed and mixed with 20 ml water three times per day for 3 weeks. All patients were instructed to rinse and hold the medication in their mouths for at least 2–3 minutes and then expectorate. Participants were evaluated at weeks 0, 3, 4, and 7. Symptoms were recorded with a 100-mm VAS; other assessments included the Treatment Satisfaction Questionnaire for Medication-9, comparisons of clinical photographs, and self-assessment via patient daily diary (Appendix 2) entries to record compliance with each dose. Results showed the compounded dexamethasone solution to be more effective compared to 0.5 mg dexamethasone tablet crushed and mixed with 20 ml water in terms of compliance, patient-perceived faster onset of action, and improved symptom relief.

1.1.3 Mucolox™

Mucolox™ is a mucoadhesive polymer gel that can be used in pharmaceutical compounding for the management of diseases and conditions of the oral mucosa including oral mucositis, and mouth ulcers^{29,30}. The safety and toxicological profile of Mucolox™ was evaluated in vitro and compared to Triton X- 100 (positive control) and distilled water (negative control), using a 3-

dimensional model of the human oral mucosa. Results showed that Mucolox™ can bind to tissues six times longer than Triton X-100 (before 50% cell viability) therefore offering increased retention of medication at the site of action. Additionally, at 4.5 hours, the difference in percent cell viability between Mucolox™ and distilled water was not significant, making it a safe water-soluble mucosal delivery system.

A recent study from our group showed that commercial dexamethasone 0.5mg/5mL solution compounded with Mucolox™ was found to be a safe option for the management of oral lichen planus when rinsed three times a day for 5-minute swish and expectorate³¹. Subjects receiving dexamethasone 0.5mg/5mL solution in Mucolox™ had a better clinical response compared to dexamethasone 0.5mg/5mL commercial solution alone (6-point reduction vs. 4.3; $p < 0.001$) of reticulation/keratosis, erythema, and ulceration (REU) scores. Both arms had a subjective improvement of the oral symptoms after 4 weeks of treatment.

2 STUDY RATIONALE

There is a significant unmet need for optimized topical therapies for Oral Inflammatory Ulcerative Diseases. Topical steroid therapy is considered the first line of treatment for Oral Inflammatory Ulcerative Diseases with current treatment regimens requiring multiple application or rinses daily^{27,32,33}. Although topical steroid therapy can be successful for most patients, the treatment schedule can be challenging to maintain. There is therefore considerable interest in developing new and more effective therapies that require less frequent applications. The possibility of having a treatment agent that is safe, easy to use, and cost effective, with potentially greater efficacy than the current standard of care available topical steroid solutions would be ideal. Using Mucolox™ as a vehicle to deliver topical dexamethasone to the oral mucosa has the potential to effectively prolong contact time between the medication and mucosa, leading to improved clinical outcomes due to the need for less frequent application. This technology would help to more efficiently achieve high drug concentrations locally. By possibly shortening the frequency and time of topical therapy and improving patient compliance, this may translate to greater therapeutic benefit. Our initial work in a small number of oral lichen planus patients has demonstrated the efficacy of dexamethasone 0.5mg/5mL solution in Mucolox™ in significantly improving signs and symptoms of OLP compared to dexamethasone 0.5mg/5mL solution only³¹. As such, dexamethasone 0.5mg/5mL solution in Mucolox™ has the potential to be used also for other Oral Inflammatory Ulcerative Diseases.

2.1 Risk / Benefit Assessment

2.1.1 Drug side effects and toxicities

Potential side effects with dexamethasone 0.5mg/5mL solution used as an oral topical rinse include an increased risk of developing oropharyngeal candidiasis and systemic absorption. All patients will be prescribed antifungal prophylaxis while on study with fluconazole 200 mg once a week. All participants will be informed that they may withdraw from the study at any time. As a topically applied agent, dexamethasone therapy can be discontinued at any time without any complications. Any noted clinical response will be expected to be reversed in such situations.

Prolonged application of potent topical corticosteroids (e.g., > 50 g of clobetasol propionate or > 500 g of hydrocortisone per week) may lead to short-term hypothalamic-pituitary-adrenal axis alteration. In our study, in case of any systemic absorption, the maximum dose would be 10.5 mg/week (5 mL x 0.1 mg/mL = 0.5 mg/rinse, 3 times/day = 1.5 mg, 7 days/week = 10.5 g). We do not expect there to be significant systemic absorption, and therefore do not expect systemic side

effects of dexamethasone solution when used as a swish and spit. Mucolox™ is a vehicle for drug delivery used in compounding medications with ingredients expected to be harmless. No major side effects from dexamethasone 0.5mg/5mL solution and dexamethasone 0.5mg/5mL solution in Mucolox™ use were reported in our first preliminary study³¹.

2.1.2 Potential benefits for participating individuals

All subjects will be assigned an active treatment. Thus, it is anticipated that the majority of participants may benefit from participation in this study. Additionally, most participants may benefit from the satisfaction in knowing that their involvement has a potential impact on the clinical care of future patients suffering from their condition.

3 STUDY OBJECTIVES

3.1 Primary Objective

The objective of this single center, 4-week, open label randomized, phase II study is to determine the clinical efficacy and tolerability of compound dexamethasone at 0.5 mg/5mL in Mucolox™ for the treatment of Oral Inflammatory Ulcerative Diseases as measured by a reduction in oral symptoms between patients treated with compounded dexamethasone 0.5mg/5ml solution in Mucolox™ (group A) and patients treated with commercial topical dexamethasone 0.5mg/5ml solution only (group B).

Completion of this study will establish important data on the efficacy of topical steroid therapy when combined with a carrier and delivery system such as Mucolox™.

3.2 Secondary Objectives

The secondary objectives are:

- To determine the clinical improvement in clinician-reported outcome measures achieved by treatment with topical compounded dexamethasone at 0.5 mg/5 mL in Mucolox™ compared to commercial dexamethasone 0.5mg/5ml solution alone.
- To assess the tolerability of Oral Inflammatory Ulcerative Diseases as measured with the 14-item Oral Health Impact Profile (OHIP-14).

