13.1 Study design/Endpoints

The primary objective of this open label randomized phase II study is to evaluate the efficacy and tolerability of topical compounded dexamethasone solution in a Mucolox™ for the treatment of Oral Inflammatory Ulcerative Diseases. The primary endpoint will be a change from pre to post treatment in each subject's subjective sensitivity score (0-10) evaluated at baseline and 4 weeks post treatment for each arm. We will also compare changes of the daily subject's subjective sensitivity score (0-10) over time for each arm.

The secondary objectives include the evaluation of objective data using the REU scoring system and the oral health related quality of life using the OHIP-14.

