13.1.2 Analysis of Secondary Endpoints

Oral health related quality of life will be assessed before and after topical therapy using the 14-item Oral Health Impacts Profile (OHIP-14; see Appendix 5) instrument that measures subject's perceptions of the impact of oral conditions on their well-being. The OHIP-14 scores will be summarized descriptively for each arm at pre-treatment, post-treatment, and pre-to-post treatment change. The pre-to-post treatment change for each item and for all items combined will be assessed within each arm using either paired t test or Wilcoxon-signed-rank test depending on its distribution. In addition, each question will be dichotomized and classified as 'response' if the answer is 'not at all', or 'slightly' to a question such as "how isolated do you feel as a result of this oral condition", and pre-to-post treatment improvement will be assessed using McNemar's test within each arm.

In order to evaluate the clinical improvement in clinician-reported outcome measures for Oral Inflammatory Ulcerative Diseases, REU scores within the compound dexamethasone solution in Mucolox™ group (Arm A) will be compared to that in the dexamethasone solution only group (Arm B). The REU scores will be summarized descriptively for each arm at pre-treatment, post-treatment, and pre-to-post treatment change. The pre-to-post treatment change will be compared between the arms using either student's t-test or Mann-Whitney test, depending on the distribution of the data.

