This document is confidential. Do not disclose or use except as authorized.

OBJECTIVE DATA (REU score)

Site	Reticular area			Erythematous area			Ulcerative area			
	0	1	2	0	1	2	0	1	2	3
Upper/lower labial mucosa	0	1	0	1	2	3	0	1	2	3
Right buccal mucosa	0	1	0	1	2	3	0	1	2	3
Left buccal mucosa	0	1	0	1	2	3	0	1	2	3
Dorsal tongue	0	1	0	1	2	3	0	1	2	3
Ventral tongue	0	1	0	1	2	3	0	1	2	3
Floor of mouth	0	1	0	1	2	3	0	1	2	3
Hard palate mucosa	0	1	0	1	2	3	0	1	2	3
Soft palate/tonsillar pillars	0	1	0	1	2	3	0	1	2	3
Maxillary gingiva	0	1	0	1	2	3	0	1	2	3
Mandibular gingiva	0	1	0	1	2	3	0	1	2	3
Total										

(R: 0 = not present, 1 = present; E & U: 0 = not present, 1 = <1cm², 2 = 1 - 3cm², 3 = >3cm²)

Total Score:

Total Weighted Score:

PHOTOGRAPHS TAKEN (circle): YES NO

CONFIDENTIAL

This document is confidential. Do not disclose or use except as authorized.

Appendix 4

DEXAMETHASONE RINSE AND MUCOLOX™ FOR THE TREATMENT OF ORAL INFLAMMATORY ULCERATIVE DISEASES

VISIT #2

Subject Name _____

Medical Record Number _____

[figure not shown]
Date of Visit _____

SUBJECTIVE DATA (Over last one week unless specified)

MUCOSAL PATHOLOGY

- 1. Does your mouth hurt now? Y/N
- 2. Does it hurt to swallow food or drink? Y/N

3. How would you rate your worst mouth sensitivity over the last week?

No sensitivity

Worst sensitivity

4. Do you avoid any foods because they make your mouth hurt?

- 0 = Not at all
- 1 = Slightly
- 2 = Moderately
- 3 = Quite a bit
- 4 = Extremely

[figure not shown]
[figure not shown]
CONFIDENTIAL

This document is confidential. Do not disclose or use except as authorized.

If “yes”, what types of foods?

- a. Spicy foods
- b. Acidic foods
- c. Salty foods
- d. Hard/crunchy/crusty foods
- e. Other:

5. Do you feel that your oral intake (what you eat) is limited by your oral condition? Y/N

Not limited at all

Severely limited

Score: _____

If “Yes”, how limited do you feel it is?

- a. Partial limitation
- b. Severe limitation

[figure not shown]
6. Have you been bothered by ulcers in the mouth?

- 0 = Not at all
- 1 = Slightly
- 2 = Moderately
- 3 = Quite a bit
- 4 = Extremely

7. Rate your level of comfort while rinsing with the topical therapy:

[figure not shown]
CONFIDENTIAL

This document is confidential. Do not disclose or use except as authorized.

[figure not shown]
Score: _____

8. Rate the taste of the topical treatment:

Score: _____

9. Rate how your mouth feels since starting topical therapy:

Score: _____

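### Tolerability of the Mucolox rinse is in the primary objective, but neither measure named in the objectives captures it, OHIP-14 is tested only within arms, and the rinse ratings have no specified analysis

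*Combined protocol and SAP*

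**What the plan says.** The primary objective (Section 3.1, repeated in the synopsis) is to "determine the clinical efficacy and tolerability of compound dexamethasone at 0.5 mg/5mL in Mucolox™", and the measure attached to it is "as measured by a reduction in oral symptoms between patients treated with compounded dexamethasone 0.5mg/5ml solution in Mucolox™ (group A") and the commercial-solution group. Section 13.1 again gives the primary objective as to "evaluate the efficacy and tolerability of topical compounded dexamethasone solution in a Mucolox™".

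OHIP-14 enters through the secondary objective in Section 3.2: "To assess the tolerability of Oral Inflammatory Ulcerative Diseases as measured with the 14-item Oral Health Impact Profile (OHIP-14". The synopsis endpoints and Sections 5.2, 13.1 and 13.1.2 describe the same instrument as oral health-related quality of life.

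Section 13.1.2 summarises OHIP-14 descriptively by arm before treatment, after treatment and as change. The change for each item and for the total "will be assessed within each arm using either paired t test or Wilcoxon-signed-rank test", depending on distribution. Each item is also dichotomised and tested within each arm by McNemar's test. VAS change (Section 13.1.1) and REU change (Section 13.1.2) are compared between arms.

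The Visit 2 form (Appendix 4) includes item 7, "Rate your level of comfort while rinsing with the topical therapy", and item 8, "Rate the taste of the topical treatment". The diary records adverse effects such as burning (Section 9.2.4). Section 9.2.3 says that tolerability will be evaluated. Section 12 refers to a toxicity report, and Section 13 promises a detailed SAP before the final analysis.

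**The concern.** A named part of the primary objective has no measure that answers it. Symptom reduction is efficacy. OHIP-14 records how the mouth condition affects daily life. An effective rinse that patients found unpleasant could improve both, and neither would show the unpleasantness.

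The OHIP-14 analysis has its own gap. Both arms receive dexamethasone at the same concentration and schedule, so the randomised contrast is the formulation. Entry requires a worst sensitivity score of at least 7 in the past week, so some improvement is expected in both arms from regression to the mean as well as from the steroid. A small p-value within each arm says nothing about the vehicle. Nor does significance in one arm and not in the other, because that is not a comparison of the arms.

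At stake is whether the trial can say anything specified in advance about how well patients tolerate the new formulation, and whether it affects quality of life differently from the commercial solution.

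**Working it through.** **1. Stated measures against what they capture**

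| Source | Measure | What it captures |
|---|---|---|
| Section 3.1 | Reduction in oral symptoms | Efficacy |
| Section 3.2 | OHIP-14 | Impact of the oral condition; no item in Appendix 5 concerns the rinse |
| Appendix 4, items 7 and 8 | Comfort while rinsing; taste | Tolerance of the rinse |
| Diary and CRF | Adverse effects | Tolerance and safety |

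The first two rows are named in the objectives. The last two bear directly on the rinse, and neither has a summary or comparison in Section 13.

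**2. Count of planned OHIP-14 tests (Section 13.1.2)**

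- Paired t or Wilcoxon signed-rank: (14 items + 1 total) × 2 arms = 30.
- McNemar: 14 items × 2 arms = 28.
- Within-arm total: 30 + 28 = 58.
- Between-arm tests: 0.
- Specified analyses of items 7 and 8: 0.

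**3. The plan's own sample size (Section 13.2)**

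The plan gives no figure for tolerability or OHIP-14. Its 15 per arm rests on VAS alone: difference 2.0, SD 1.4, two-sided 0.05, at least 80% power, 5% loss. The standardised difference is 2.0/1.4 = 1.43. An exact t-test calculation gives 9 per arm, or 10 after 5% loss, so these inputs do not reproduce 15. Power at 15 per arm is 96.5%, so the stated minimum is met. This neither supports nor weakens the present point.

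**4. What a between-arm comparison of scores could show at the planned size**

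After 5% loss, 15 × 0.95 = 14.25, so 14 to 15 per arm. For an unadjusted t-test (two-sided 0.05, 80% power), the normal approximation to the detectable standardised difference is (1.960 + 0.842) × √(2/n), and the exact value comes from the noncentral t. The half-width of the 95% confidence interval is t(0.975, 2n − 2) × √(2/n).

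| n per arm | Normal approximation | Exact | CI half-width |
|---|---|---|---|
| 15 | 2.802 × 0.365 = 1.02 SD | 1.06 SD | 2.048 × 0.365 = 0.75 SD |
| 14 | 2.802 × 0.378 = 1.06 SD | 1.10 SD | 2.056 × 0.378 = 0.78 SD |

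The documents give no SD for OHIP-14 or for items 7 and 8. Multiplying the exact values by assumed SDs gives:

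| Assumed SD (points) | Detectable, 15 per arm | Detectable, 14 per arm |
|---|---|---|
| 1.5 | 1.59 | 1.65 |
| 2.0 | 2.12 | 2.20 |
| 2.5 | 2.65 | 2.75 |
| 3.0 | 3.18 | 3.30 |

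Baseline adjustment would tighten the OHIP-14 estimate by an amount that depends on the correlation between baseline and week 4, which the documents do not give.

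**The case against.** The strongest reply is that much of this is one badly worded sentence. The literal object of the secondary objective is the disease, which a disease-impact instrument fits. The endpoint and statistics sections already call OHIP-14 quality of life, and no analysis text says that an improvement in it will be reported as tolerance of the rinse. That is fair, and it makes the relabelling a correction of wording. It does not supply a measure for the tolerability named in Sections 3.1 and 13.1.

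A second reply is that tolerability is covered: Section 9.2.3 promises an evaluation, adverse events are graded and assigned causality, Section 12 mentions a toxicity report, and a detailed SAP is to follow. A reader might infer from Section 13 that comfort and taste will go unanalysed. The documents do not support that; they support only that no method is specified. The gap still matters, because in an open-label trial a tolerability measure chosen after data accrue is open to selection.

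A third reply is that by-arm summaries let anyone take the OHIP-14 difference. They do, but the plan gives no formal between-arm estimate with an interval, although it compares the arms on VAS and REU.

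Finally, 30 patients are too few for a firm between-arm conclusion. That stands, and it is why these comparisons should be labelled descriptive. The particular test used for items 7 and 8 is a matter of preference.

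**Conclusion.** The point holds as a gap in objectives and analysis. The objectives name two measures in connection with tolerability, and neither measures tolerance of the rinse. OHIP-14 has 58 planned within-arm tests and no between-arm test. The data that bear on tolerability are collected without a specified summary or comparison.

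Three stronger readings are tempting and are not supported:

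- That the tolerability in the primary objective is assigned to OHIP-14. Section 3.1 ties it to symptom reduction; OHIP-14 belongs to the secondary objective.
- That comfort and taste are main reasons for the vehicle. The rationale rests on contact time, less frequent application, compliance and efficacy. Rinse comfort is not mentioned, and taste appears once, in Section 1.1.1, as a general obstacle with topical steroids.
- That ratings will exist for all 30 patients. Items 7 and 8 are on the Visit 2 form only, so they cover those who attend Visit 2 or an early discontinuation visit that follows its procedures.

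The size of the addition is modest: about 1.1 SD detectable at 80% power, with intervals of about ±0.75 to ±0.78 SD. These figures assume an unadjusted t-test with 14 to 15 evaluable per arm. The response scales of items 7 and 8 are in figures that are not reproduced, so the results cannot be tied to their anchors. The primary VAS comparison is unaffected.

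**What to change.** 1. Reword the secondary objective in Section 3.2 and the synopsis so that OHIP-14 measures oral health-related quality of life, as the endpoint sections already say.
2. In Section 13.1.2, make the main OHIP-14 analysis a between-arm comparison of the week 4 total score adjusted for the baseline total (ANCOVA), reported as a difference with a 95% confidence interval. The within-arm results can stay as description.
3. Base tolerability on Visit 2 items 7 and 8 and on treatment-related oral adverse events, each reported by arm with the between-arm difference and a 95% confidence interval.
4. Count adverse events in all treated patients, including those later replaced (Section 12.4) or classed as unevaluable (Section 12), so that patients who stop because of intolerance stay in the tolerability report. State how many patients in each arm lack items 7 and 8.
5. Label all of these comparisons descriptive, and put them in the protocol or the SAP before outcome data are examined.

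The cost is revised objective wording and a few lines of analysis. No new data, visits or patients are needed. The estimates will be imprecise.

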4 STUDY DESIGN

4.1 Study Overview

This is a single center, 4-week, open label randomized, phase II study. Randomization will be conducted by the UCSF Investigational Drugs Services (IDS) Pharmacy. The study period will be four weeks, which based on previous studies should be an adequate period to assess significant clinical improvement. Subjects will be evaluated clinically at baseline before starting treatment and at the end of the four-week period, for a total of two visits. Subjects will be randomized to either compounded dexamethasone in Mucolox™ or commercial dexamethasone solution only. Subjects will return for evaluation after four weeks at which time the primary end-points will be assessed. Screening data will be reviewed to determine subject eligibility. Subjects who meet all inclusion criteria and none of the exclusion criteria will be entered into the study.

The following treatment regimens will be used:

Experimental treatment: Dexamethasone solution (0.5mg/5ml) in Mucolox™

Comparator: Commercial Dexamethasone solution (0.5mg/5ml)

Total duration of subject participation will be four weeks. Total duration of the study is expected to be 4-5 weeks.

5 CRITERIA FOR EVALUATION

5.1 Primary Efficacy Endpoint

The primary endpoint will be a change from pre to post treatment in each subject's subjective sensitivity score (0-10) evaluated at baseline and 4 weeks post treatment for each arm. We will also compare changes of the daily subject's subjective sensitivity score (0-10) over time for each arm.

5.2 Secondary Efficacy Endpoints

The secondary objectives include the evaluation of objective data using the REU scoring system and the oral health related quality of life using the OHIP-14. For the analysis of secondary endpoints see the statistical section.

5.3 Safety Evaluations

The safety of participants and the overall study will be monitored continuously throughout the study period. At the 4 week visit, evaluating physicians will review the participants' diaries for self-reported adverse events. Subjects will be instructed to contact their treating physician by phone or email to report any unexpected side effects or side effects lasting more than 7 days, should they occur. Any necessary medical intervention will be handled by the treating physician. Data accuracy and protocol compliance will be monitored and assured by the Principal Investigator and toxicities will be reported promptly to the IRB

